Sample size and power considerations. To determine sample size, we started at the right of the schematic in Figure 1 (the second randomization) and moved from right to left to determine the needed number of consenting dyads. To power the comparisons on primary outcomes for the groups created by the second randomization (Aim 2), we used the effect size of Cohen’s $d=0.39$ (adjusted for baseline), the smallest seen in the preliminary data for TIP-C against an educational intervention (Table 1) to conservatively estimate sample size requirements. We further adjusted this effect size for the reduction in error variance due to 10 repeated measures of primary outcomes. In past studies, Pearson correlation coefficients between pairs of repeated measures of depression, anxiety and summed severity of other symptoms ranged from $r=0.36$ to 0.77, resulting in the range of the adjusted effect sizes from $d=0.54$ to 0.84. Using the smallest adjusted $d=0.54$, the required sample size is 60 per group created by the second randomization, for power of .80 or greater in two-tailed tests at the 0.05 level of significance.

Moving from left to right in Figure 1 (schematic), 120 dyads from two groups created by the second randomization will be non-responders to the SMSH alone. From past work, response rate to the SMSH on depression and anxiety was approximately 30%,²²⁸ therefore 120 non-responders will be 70% of 172 randomized to the SMSH alone in the first randomization. The comparison of these 172 to 60 dyads allocated to the TIP-C+SMSH in the first randomization will have power of 0.95 to detect the effect size of 0.54 (adjusted for the repeated measures) in testing the hypothesis associated with Aim 1. The tests of mediation and interdependence effects in Aim 3 will have an even greater power because of further reduction in error variance. Aim 4 is exploratory, thus formal power considerations are not applicable. In summary, the total

required post-attrition sample size for all specific aims is N=232. To account for 22% attrition based on past work, we will need 298 dyads to consent.

Recruitment and retention of participants.

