Aim 1, Hypothesis 1: Dyads initially randomized to the TIP-C+SMSH will report lower depression, anxiety, and summed severity of other symptoms at weeks 1-12, 13, and 17, and lower unscheduled health services use, higher self-efficacy and social support, and lower caregiver burden at weeks 13 and 17 as compared to those initially randomized to the SMSH alone. This hypothesis will be tested using statistical model #1 that relates repeated measures of the survivor or caregiver outcome y (one at a time) to the group assignment variable xx_1 , outcome at baseline xx_2 , time entered as a class variable to model potentially non-linear patterns, and other covariates. For normally distributed outcomes, this model will be fit as a linear mixed effects model (LME). Generalized linear mixed effects (GLME) modeling will be used if outcome is not normally distributed and cannot be normalized using transformations. For health service use, statistical model #1 will be implemented as a GLME model with Poisson distributed errors, or as a zero-inflated Poisson or negative Binomial model based on the distribution of the counts of different health services uses. Each type of health services use (e.g., hospitalizations, ED visits) will be analyzed separately. The explanatory variables including study group will be evaluated as predictors of zero inflation (whether or not the count is zero), and also as predictors of the magnitude of the count when it is not zero. The main effects of the group variable xx_1 will be tested.

Aim 2, Hypothesis 2: Dyads where survivors do not respond to the SMSH alone during weeks 1-4 and have TIP-C added during weeks 5-12, will report lower depression, anxiety, and summed severity of other symptoms at weeks 5-12, 13, and 17, and lower unscheduled health services use, higher self-efficacy and social support, and lower caregiver burden at weeks 13 and 17 as compared to those who are re-randomized to continue with the SMSH alone. The strategy described under the analyses for Aim 1 will be implemented for the repeated outcome measures during weeks 5-12 and weeks 13 and 17 that will be related to group assignment from the second randomization, symptom severity during week 4, time, and covariates.

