6.0 MEASURES/DATA COLLECTION INSTRUMENTS

Describe all forms, questionnaires, instruments or other specific methods used to collect data. Include complete copies of all forms, interview guides, survey questionnaires, in Appendix I.

Measures

Patient Reported Outcomes Measurement Information System (PROMIS)²⁴⁹ measures are suitable for both survivors and caregivers, have been developed using sophisticated measurement techniques, tested with over 21,000 individuals, calibrated to produce T-scores based on the general population, and are available in either English or Spanish. The available short forms have evidence of good reliability and validity.²⁴⁹ Our other measures also have good reliability ($\alpha > .80$)^{41,84,178,205} and validity, have been translated²⁴⁰ and tested with Spanish speaking participants in our pilot studies.³¹

Primary outcomes.

Caregivers' and survivors' symptoms will be measured using the adapted General Symptom Distress Scale (GSDS),^{124,250} a brief instrument that allows for a quick assessment of symptoms, which is especially important during weekly calls. It evaluates 15 symptoms: shortness of breath, nausea, vomiting, pain, sleep difficulties, bowel problems, numbness or tingling, skin rashes or sores, swelling in hands and feet, difficulty concentrating, poor appetite, cough, depression, anxiety, fatigue. Respondents indicate presence of each symptom (yes/no) and rate their severity on the scale from 1 to 10. The ability to manage symptoms is also assessed on a scale from 1=cannot manage to 10=can manage extremely well. The GSDS has good test-retest and internal consistency reliability and predictive and construct validity in both English and Spanish.²⁵⁰ The 0-10 ratings of depression and anxiety and the summed severity of other 13 symptoms will be derived at each weekly contact, baseline, 13, and 17 week interviews.

Survivors' symptom response on depression and/or anxiety during weeks 1-4 as a criterion for rerandomization.

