Potential problems from recruitment and retention will be minimized by the use our previous methods yielding high retention rates with no differential attrition between conditions. Potential problems in intervention delivery will be minimized by implementing protocols to maintain intervention fidelity. There are no high-risk aspects of this trial, and all procedures are non-invasive. We recognize that in addressing depression and anxiety our efforts might inadvertently produce detrimental psychological responses. Should this occur, our experienced interventionists will refer the survivor and/or caregiver to mental health services. Because randomizations may not account for all possible error sources, we will adjust for baseline values of outcomes in the analysis to provide added control over possible confounding preintervention influences. Three primary outcomes (depression, anxiety, and summed severity of other symptoms) and all hypotheses are stated a priori. In the exploratory analyses, the Benjamini-Hochberg or Hochberg adjustment²⁷⁷⁻²⁷⁹ will be used to control the false discovery rate.

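### The Aim 2 model sentence names only week-4 severity as its pre-re-randomisation term; baseline and week 1–3 values already scheduled could sharpen the comparison at almost no cost

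*Combined protocol and SAP*

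**What the plan says.** The Aim 2, Hypothesis 2 paragraph in Section 5.0 (repeated in Section 8.0) carries over the Aim 1 strategy and then lists its own terms: outcomes at weeks 5–12, 13 and 17 are "related to group assignment from the second randomization, symptom severity during week 4, time, and covariates". The Aim 1 model lists the outcome at baseline; the Aim 2 list does not.

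Section 6.0, Primary outcomes, says the depression and anxiety ratings and the 13-symptom sum "will be derived at each weekly contact, baseline, 13, and 17 week interviews". Section 7.0 schedules the GSDS weekly for caregivers too. Weeks 0, 1, 2 and 3 are therefore scheduled before week 4, and all five readings precede the second randomisation.

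Other outcomes follow a sparser schedule. PROMIS depression and anxiety, self-efficacy, social support, caregiver burden and service use are collected in the interviews at baseline and weeks 13 and 17 (Section 6.0). They have a week-0 value and no week-4 value.

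Two other places bear on the model. Section 8.0, Potential Difficulties, says "we will adjust for baseline values of outcomes in the analysis to provide added control over possible confounding preintervention influences", without limiting this to Aim 1. The mediation models for Aims 1 and 2 adjust for the baseline symptom outcome.

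**The concern.** Aim 2 is the comparison from which the sample size was built. In a randomised comparison, any covariate measured before randomisation can be adjusted for without bias, and an informative one shrinks the error variance. The Aim 2 sentence names one such reading when up to five are scheduled.

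There is also a specification gap that does not depend on any correlation. The sentence covers all Aim 2 outcomes, but its adjustment term is a symptom score. Taken literally, caregiver burden or PROMIS depression would be adjusted for week-4 symptom severity and not for its own baseline. Section 8.0 points the other way. Two analysts could fit different models and each cite the plan.

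**Working it through.** **The plan's own figure.** Section 4.0 says: "Using the smallest adjusted $d=0.54$, the required sample size is 60 per group created by the second randomization". The test is two-sided at 5%, and the target is at least 80% power. Under the normal approximation, n = 2(1.960 + 0.842)²/0.54² = 53.8, so 54 per group (55 with the t distribution). Sixty per group gives power 0.841 (normal) or 0.835 (t). The claim of at least .80 is true, with a small margin.

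**Inputs.** Ten post-re-randomisation occasions (weeks 5–12, 13, 17). Pairwise correlations "ranged from $r=0.36$ to 0.77, resulting in the range of the adjusted effect sizes from $d=0.54$ to 0.84" (Section 4.0). No correlation structure over time is given, so I treat it as an assumption and show the range. Scores are standardised to variance 1.

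**Quantity.** The variance of the 10-occasion mean conditional on the pre-randomisation covariates: V = Var(mean) − c′S⁻¹c, where c holds the covariances of the covariates with that mean and S is the covariates' covariance matrix.

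**Exchangeable case, by hand.**
- Week 4 only: (1 + 9r)/10 − r². At r = 0.36: 0.4240 − 0.1296 = 0.2944. At r = 0.77: 0.7930 − 0.5929 = 0.2001.
- Week 4 plus the mean of weeks 0–3: (1 + 9r)/10 − 5r²/(1 + 4r). At 0.36: 0.4240 − 0.2656 = 0.1584. At 0.77: 0.7930 − 0.7266 = 0.0664.
- Weeks 0 and 4 only: (1 + 9r)/10 − 2r²/(1 + r). This gives 0.2334 and 0.1231.

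**All structures.** Correlation at lag k is shown in the first column.

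| Structure | Week 4 | Week 4 + mean of weeks 0–3 | Reduction | Weeks 0 and 4 | Reduction if week 0 is already in |
|---|---|---|---|---|---|
| Exchangeable, 0.36 | 0.2944 | 0.1584 | 46% | 0.2334 | 32% |
| Exchangeable, 0.77 | 0.2001 | 0.0664 | 67% | 0.1231 | 46% |
| Mixed, 0.5r + 0.5rᵏ, r = 0.36 | 0.2608 | 0.2182 | 16% | 0.2401 | 9% |
| Mixed, r = 0.77 | 0.3403 | 0.3031 | 11% | 0.3129 | 3% |
| Decaying, 0.77φᵏ⁻¹, φ = (0.36/0.77)^(1/16) | 0.3130 | 0.2746 | 12% | 0.2953 | 7% |
| Decaying, 0.36 + 0.41 × 0.7ᵏ⁻¹ | 0.3498 | 0.3163 | 10% | 0.3215 | 2% |
| AR(1), r = 0.77 | 0.3731 | 0.3731 | 0% | 0.3731 | 0% |

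**Selection of non-responders.** A simulation with illustrative cut-offs (baseline above average, week 4 above the 30th percentile) gave variance ratios, all five readings against week 4 alone, of 0.61 and 0.38 (exchangeable), 0.89 (decaying) and 1.00 (AR(1)). Selection does not change the picture.

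**Power, as illustration.** If d = 0.54 is taken as the week-4-only value (an assumption), the equivalent d is 0.54/√(variance ratio). For the mixed and decaying rows this is about 0.57–0.59, and power at 60 per group moves from 0.84 to about 0.87–0.90.

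**Interview outcomes.** For the mean of weeks 13 and 17, assume that week-4 GSDS severity correlates c = 0.2–0.5 with the outcome at each occasion, and that the outcome's own occasions correlate r. Week-4 GSDS alone leaves (1 + r)/2 − c². Adding the own week-0 value leaves (1 + r)/2 − (r² + c² − 2rc²)/(1 − c²). At r = 0.36 and c = 0.2 these are 0.6400 and 0.5333, a ratio of 0.83. Over c = 0.2–0.5 the ratio is 0.83–0.96 at r = 0.36 and 0.34–0.43 at r = 0.77. The plan's r range is for symptoms, so its use here is a further assumption, and service-use counts are not covered.

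**Cost.** With 120 dyads, one extra covariate raises the variance by roughly 115/114, about 1%. Entering weeks 0–3 as four separate terms would cost 115/111, about 3.6%.

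**The case against.** A reader might infer that the model uses week 4 and nothing else. The documents do not establish that. Aim 2 inherits a strategy that contains the baseline outcome, its list ends with unnamed covariates, and the Section 8.0 statement speaks of randomisations in the plural. Even the planning effect is "d=0.39$ (adjusted for baseline), the smallest seen in the preliminary data for TIP-C". Week 0 may well be intended, and for interview outcomes the point would then reduce to unclear wording. This stands, and it is why the smaller gains are shown. Weeks 1–3 still appear nowhere in the model.

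A reader might also infer that precision is certainly lost, and by a half or more. The 46–67% figures need the same correlation at every lag. A range of 0.36 to 0.77 across pairs and outcomes fits decay at least as well, and under AR(1) the earlier readings add nothing. This stands too.

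Nor does every re-randomised person necessarily have all five readings. Section 7.0 allows for missed weekly calls, so these readings are scheduled, not guaranteed.

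It is also tempting to call week 4 a noisy, range-restricted single item. That does not describe the 13-symptom sum, and selection acts directly only on survivors' depression and anxiety. A correlation of 0.36 may reflect a long lag and not noise.

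Finally, week-4 adjustment is valid. There is no bias and no effect on type I error, and 60 per group already meets the stated power. That is correct, and the point is one of efficiency and clarity.

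**Conclusion.** The point holds as a free improvement, not as an error that threatens Aim 2. The specification gap is firm: the Aim 2 sentence names week-4 severity alone, weeks 1–3 are unused, interview outcomes have no week-4 value of their own, and the Section 8.0 statement on baseline adjustment is not reconciled with it.

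The gain in precision is conditional. For GSDS outcomes it is about 10–16% of error variance under mixed or decaying correlation. If week 0 is already in the model it is about 3–9%, or 2% in the least favourable decaying curve shown. It is 46–67% under exchangeable correlation with week 4 alone as the comparator, and nil under AR(1). These figures rest on the plan's range of r and on assumed structures.

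**What to change.** In the Aim 2 paragraph of Sections 5.0 and 8.0, replace the week-4 term with two statements:

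- GSDS outcomes are adjusted for the week-4 score plus that person's mean of the available baseline and weeks 1–3 scores on the same outcome. Baseline precedes the first randomisation, so this mean can be formed even when calls in weeks 1–3 are missed, and nobody is dropped for that reason.
- Interview outcomes (PROMIS depression and anxiety, self-efficacy, social support, caregiver burden, service use) are adjusted for their own week-0 value plus week-4 GSDS severity.

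Make the baseline-adjustment statement under Potential Difficulties in Section 8.0 refer to this rule. The cost is a short change to the text and about one degree of freedom per model. No new data are needed, and the sample size does not change.

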Specific aims: **1)** Determine if dyads in the TIP-C+SMSH as compared to the SMSH alone group created by the first randomization will have: a) lower depression, anxiety, and summed severity of 13 other symptoms at weeks 1-12, 13, and 17 (primary outcomes); b) lower use of healthcare services (hospitalizations, urgent care or emergency department [ED] visits) during 17 weeks (secondary outcomes); c) greater self-efficacy, social support, and lower caregiver burden during weeks 13 and 17 (potential mediators). **2)** Among nonresponders to the SMSH alone after 4 weeks, determine if dyads assigned to TIP-C+SMSH as compared to the SMSH alone group created by the second randomization will have better primary and secondary outcomes and potential mediators at weeks 5-12, 13, and 17. **3)** Test the interdependence in survivor's and caregiver's primary and secondary outcomes. **4)** Determine which characteristics of the dyad are associated with responses to the SMSH alone during weeks 1-4 and optimal outcomes for the dyad during weeks 1-12, 13 and 17 so as to determine tailoring variables for the decision rules of individualized sequencing of interventions. Findings will be used to improve symptom management and reduce distress in survivor-caregiver dyads.

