Mediation analyses for Aims 1 and 2. To test for mediation, the study group will be treated as the independent variable, and each of the potential mediators (one at a time) will be tested for their effect on the symptom outcome variable at weeks 13 and 17, with the baseline measure of that respective symptom outcome variable treated as a covariate. Caregiver burden will be tested only at the individual level, but social support and self-efficacy will be tested at the individual and dyadic levels. We will use a bias corrected bootstrapping analytic strategy^{267,268} based on 5000 bootstrap samples to estimate confidence intervals around the indirect effect of study group on the outcome variable, through the mediator. To establish mediation, the 95% confidence interval around the indirect effect must not include 0.

Aim 3 examines the dyadic interdependence in outcomes between survivors and caregivers. This interdependence will be modeled and tested with the actor-partner interdependence mediation model (APIMem)²⁶⁹ in structural equation modeling. The APIMem estimates three classes of effects: actor effects (e.g., person A independent variable (IV) \rightarrow person A dependent variable (DV)), caregiver (partner) effects (e.g., person A IV \rightarrow person B DV), and mediation effects (e.g., person A IV \rightarrow person B Mediator \rightarrow person A DV) in an omnibus model. These models will specify correlations between the survivors' and caregivers' IVs as well as covariances between the error terms of the mediators and outcome variables, recognizing that these residuals will covary between dyad members due to unmeasured common causes. We will fit both a saturated version of the model in which all actor, partner, and mediation effects are free to vary and compare that with a

constrained model in which the effects for one dyad member are constrained equal to the corresponding effects of the other dyad member. The χ^2 difference test will determine whether the more parsimonious constrained model or the unconstrained model will be interpreted. This test will also indicate whether the effect for survivors is significantly different from that of caregivers. These models will test whether baseline to week 17 changes in survivors' outcomes of depression, anxiety and summed severity of other symptoms are mediated by the intervening (week 13) state or caregivers' outcomes or potential covariates.

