Secondary outcomes. Secondary outcomes are caregivers' and survivors' hospitalizations, urgent care or ED visits during the study. In baseline, week 13 and 17 interviews over the telephone, each dyad member will be asked to recall ED visits and admissions to hospitals and, if they occurred, their reasons and duration. Recall period will be 3 months in baseline and week 13, and 1 month in week 17 interviews. Extensive previous research²⁻⁵ documents self-report is a reliable and valid method to collect health services use data especially when standardized methods are used and the recall period is short, as in this project. Self-report is the only reasonable and cost-effective way to assess healthcare use, as it would be impossible to access health (medical) records across the multiple systems and payers used by participants in this study.

Potential mediators.

Caregivers' and survivors' self-efficacy. PROMIS 4-item short forms (sf) will be administered in interviews.²⁵³⁻²⁵⁶ Self-efficacy specific to symptom management will be captured by the GSDS item described above.

Caregivers' and survivors' social support. PROMIS 4-item-sf for emotional support and PROMIS Informational Support 4a will be used in interviews.²⁵³⁻²⁵⁶

Caregiver Reaction Assessment Tool.²⁵⁷ This caregiver burden tool was developed and validated with caregivers of patients with chronic conditions. It has 5 subscales: impact on schedule, caregiver's esteem, family support, impact on health, and impact on finances, with Cronbach's alphas exceeding 0.70.

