Scientific Rigor and Transparency. The scientific rigor of this study is ensured by the randomized design, complete inclusion/exclusion criteria defining the population to which findings would be generalizable, reproducible manualized protocol for the interventions, tracking of intervention fidelity, dose, receipt and enactment, use of measures with solid evidence of reliability and validity, blinding of data collectors, transparent assessment and statistical analysis plans including attention to biases and the missing data.

Sex as a biological variable. We will consider survivors' and caregivers' sex as covariates in all analyses. Past research indicates that the survivor-caregiver relationship (spouse/partner versus other) is a key factor that may influence outcomes^{62,165} for the dyad over and above sex. Relationship will be controlled in randomization and considered along with sex as a covariate and potential future tailoring variable.

Analytic Methods

Data management. All data will be entered into the secure web-based database. Quarterly quality assurance checks of the data will be performed by the RA supervised by [name]. De-identified data will be transferred into SAS 9.4 for analyses. The distributions of outcomes and potential covariates will be assessed, outliers will be investigated by inspecting the residuals, and models described below will be fit with and without outliers to examine their influence on the results.

Attrition Analyses and Handling of Missing Data. We will compare dyadic characteristics of those who completed the study to those who did not within their designated group to inform the generalizability of findings. Attrition will also be compared between each pair of randomized groups. The regression techniques described below allow for missing at random (MAR) mechanism.²⁶⁴ If patterns of missing data indicate potential not missing at random (NMAR) mechanisms, then models describing missing mechanisms will be considered (e.g., pattern-mixture models),^{265,266} and sensitivity analyses will investigate the robustness of the results.

Primary Analysis. Primary analyses will follow the intent to treat approach.

Aim 1, Hypothesis 1: Dyads initially randomized to the TIP-C+SMSH will report lower depression, anxiety, and

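### The Aims 1 and 2 mediation model leaves out the baseline mediator, and its confidence-interval rule cannot by itself establish mediation

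*Combined protocol and SAP*

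**What the plan says.** The paragraph on mediation for Aims 1 and 2 appears in section 5.0 (Analytic Methods) and again in section 8.0. Study group is the independent variable. Mediators are taken one at a time, and each "will be tested for their effect on the symptom outcome variable at weeks 13 and 17". The paragraph names one adjustment term, so that the model is fitted "with the baseline measure of that respective symptom outcome variable treated as a covariate". The interval is a bias-corrected bootstrap "based on 5000 bootstrap samples". The decision rule for establishing mediation is that "the 95% confidence interval around the indirect effect must not include 0".

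Section 2.0 dates the mediators: "greater self-efficacy, social support, and lower caregiver burden during weeks 13 and 17 (potential mediators". Hypotheses 1 and 2 use the same weeks. The mediation paragraph gives no lag, no baseline-mediator term and no sensitivity analysis for causes common to mediator and symptom.

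Three other statements bear on this:
- Section 8.0, on sex as a biological variable: "We will consider survivors' and caregivers' sex as covariates in all analyses".
- Statistical model #1 adjusts each outcome for its own baseline, and Hypothesis 1 lists the mediators among the outcomes tested with that model. Section 6.0 says of self-efficacy that "PROMIS 4-item short forms (sf) will be administered in interviews", and interviews take place at baseline, week 13 and week 17.
- The Aim 3 dyadic model allows for correlated errors because "these residuals will covary between dyad members due to unmeasured common causes", and uses a week-13 intervening state for change to week 17. Neither feature is carried into the Aims 1 and 2 mediation test.

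**The concern.** Randomisation protects the path from group to mediator. It does not protect the path from mediator to symptom. Self-efficacy, support and symptoms are self-reported, on this reading in the same call. A stable disposition, or a bad week, can move both and look like a mediator effect. Multiplied by a genuine group effect on the mediator, this meets the plan's rule with no mediation present.

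Adjusting for the baseline symptom alone is also an awkward half-measure. It leaves baseline variation in the mediator in the error term. If the mediator really acts on the symptom, it also biases the mediator coefficient towards zero.

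At stake is the account of how TIP-C works, and the evidence on mediators that are later considered as future tailoring variables.

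**Working it through.** **Inputs.** From section 4.0: 60 v 60 (Aim 2) and 60 v 172 (Aim 1) after attrition; two-sided 0.05; correlation between repeated measures r = 0.36 to 0.77 (given for symptoms, assumed here for mediators too); d = 0.39 (given for primary outcomes, assumed here as the group effect on the mediator). Not in the documents: the mediator-symptom correlation ρ due to shared causes. It is assumed to be 0.1 to 0.5.

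**1. The plan's own figure.** The plan states no error rate for the mediation test beyond the 95% interval, so the nominal rate is 5%. As a check of the set-up, take k = √(n₁n₂/N). For 60 v 172, k = √(10320/232) = 6.670. The Aim 1 power is Φ(0.54 × 6.670 − 1.960) = Φ(1.642) = 0.95, as stated. For 60 v 60, k = 5.477.

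**2. False mediation under the planned model.** Let mediator and symptom have unit variance, the same r, shared causes of strength ρ in both their stable and same-week parts, and no effect of mediator on symptom. Given the baseline symptom:
- partial correlation p = ρ√(1−r²)/√(1−r²ρ²)
- z_b = p√(N−4)/√(1−p²)
- z_a = 0.39k/√(1−r²ρ²)
- rate ≈ Pr(path a significant) × Pr(path b significant)

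Example with N = 120, r = 0.77, ρ = 0.3: p = 0.3 × 0.638/0.973 = 0.197; z_b = 0.197 × 10.77/0.980 = 2.16, probability 0.580; z_a = 2.136/0.973 = 2.195, probability 0.593. The product is 0.34.

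| ρ | r | 60 v 60 | 60 v 172 |
|---|---|---|---|
| 0 | either | 3% | 4% |
| 0.1 | 0.36 | 10% | 22% |
| 0.1 | 0.77 | 6% | 12% |
| 0.3 | 0.36 | 51% | 74% |
| 0.3 | 0.77 | 34% | 65% |
| 0.5 | 0.36 | 58% | 75% |
| 0.5 | 0.77 | 62% | 80% |

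Simulation with a bias-corrected bootstrap (1,000 resamples, 500 to 600 trials per cell) agrees in substance. With ρ of 0.2 to 0.5 it gives 23–69% (60 v 60) and 45–83% (60 v 172). With ρ = 0.1 it gives 13–14% and 19–26%. With a mediator shift of 0.20 instead of 0.39, and ρ of 0.2 to 0.5, it gives 7–33% and 21–36%. With no group effect on the mediator it gives 3–9% and 5–7%. With no common cause it gives 0.4–8% and 0.4–7%.

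**3. What leaving out the baseline mediator costs.**
- Power for group to mediator is Φ(0.39k − 1.96) without it and Φ(0.39k/√(1−r²) − 1.96) with it. At 60 v 60, 0.57 becomes 0.63 (r = 0.36) or 0.92 (r = 0.77). At 60 v 172, 0.74 becomes 0.80 or 0.98.
- Suppose a real same-week effect b, present at every interview, and no confounding. The planned model then estimates b − b·r²/(1 + b² − b²r²). For b = 0.30 this is 0.30 − 0.036 = 0.264 (r = 0.36) or 0.30 − 0.172 = 0.128 (r = 0.77). With the baseline mediator added, the estimate is 0.30.

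**4. What adding it does not do.** With no mediator effect and ρ = 0.3, the planned model's coefficient is ρ(1−r²)/(1−r²ρ²) = 0.264 (r = 0.36) or 0.129 (r = 0.77). These are practically the values in step 3 for a real effect of 0.30, so this model cannot separate the two cases. In simulation, adding the baseline mediator cuts false mediation from a purely stable shared cause (16–52% falls to 8–22%). Where a same-week cause is also present it can raise it, because path a becomes more precise: 44% becomes 87% at 60 v 60 with r = 0.77 and ρ = 0.3.

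**5. A lagged model** (week-13 mediator to week-17 symptom, adjusted for baseline mediator, baseline symptom and week-13 symptom). With no mediator effect its false-mediation rate is 3–6% when the stable and same-week correlations are equal, and about 6–14% when they differ. With a real same-week effect of 0.3 to 0.5 and no confounding, it detects mediation in about 2–7% of trials, against 30–78% for the planned model.

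**The case against.** A reader might infer that the planned test will often declare mediation where there is none. The documents do not support that without conditions. They give no mediator-symptom correlation and no TIP-C effect on any mediator, and the rate is near nominal if either is absent. What stands is narrower: Hypotheses 1 and 2 predict that TIP-C moves these mediators, and shared causes of self-reports are plausible, so the plan cannot assume the favourable case.

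Same-week pairing is the natural reading, but it is not explicit: the mediation paragraph dates the outcome, and the mediator weeks come from the aims and hypotheses. Nor is the baseline symptom strictly the only covariate, since sex is considered in all analyses. Sex would not remove confounding by stable disposition or by the state of the week.

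A reader might also infer that the lagged model should become the main test. Step 5 argues against that. TIP-C ends at week 8 or week 12, so much of any mediation may be complete by week 13, and a null lagged result would then mislead.

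Finally, mediation is neither a primary nor a secondary comparison. Aim 4 is exploratory, does not make a significant indirect effect a condition for considering a mediator, and defers its rules to a future trial. This objection stands and limits the consequence: no Aim 1 or Aim 2 treatment comparison is affected.

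**Conclusion.** The point holds in a conditional form. As written, the rule claims more than the model can deliver. Under the assumed 0.39 SD mediator shift and correlations of 0.1 to 0.5, false mediation runs from roughly 6% to 83%, the width reflecting how little the documents say about the correlation. The loss from omitting the baseline mediator also rests on assumed values, but its direction does not depend on confounding: lower power for path a, and a real mediator effect shrunk by about 12% (0.264 for 0.30) to 57% (0.128 for 0.30). The plan should be changed, but the matter concerns the explanation of mechanism and not the trial's main conclusions.

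**What to change.** Amend the mediation paragraph in both sections 5.0 and 8.0:

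1. Add the baseline value of the mediator, alongside the baseline symptom, to both the group-to-mediator and the mediator-to-outcome models. State which week's mediator goes with which week's outcome.
2. Describe an interval excluding 0 as consistent with mediation, not as establishing it.
3. Add a sensitivity analysis for unmeasured mediator-outcome confounding. For example, refit over a grid of assumed residual correlations between the two models and report the correlation at which the interval first includes 0. This must accompany item 1, because baseline adjustment does not remove same-week confounding and can raise false positives from it.
4. Report the week-13 mediator to week-17 outcome model as a supporting sensitivity analysis, with its low power for mediation complete by week 13 stated.

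The cost is SAP wording, one extra covariate per model and some programming. No added sample is needed. Statistical model #1 already presupposes baseline mediator values. Section 6.0 does not state when the caregiver burden tool is administered, so its use at baseline should be confirmed.
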